### 5.3 Informed Consent Procedures

A Waiver of Informed Consent has been obtained to cover screening/recruitment procedures, that will allow research study staff to approach patients. Informed consent for study participation is as described below. Informed consent will be offered following screening/completion of a Screening Checklist. The Screening Checklist is provided (Attachment AA). The Screening Checklist consists of the Inclusion/Exclusion criteria stated below in Table 1. A Waiver of Documentation of Informed Consent has been approved to use an Information Statement in lieu of requiring a signed consent form.

#### A. Informed Consent:

*In the section below, all uses of the words 'patients' or 'participants' prior to completion of the informed consent process using the Information Statement refers to potential candidates for study participation. Please see the Information Statement document.*

Informed consent gives patients the opportunity to choose whether or not they want to participate in a study. Informed consent will be administered by research study staff (research assistants, research coordinator, or research specialist) who are or will be named as part of this study protocol and human subjects documentation. Research staff will have completed the necessary human subjects protections training per VA policy to engage in human subjects research and will remain current with such trainings during the study period. Any new study personnel added to the study in the future will also have been trained on VA consent procedures, and will be trained on informed consent for this study by existing research staff for this study. Adequate informed consent requires the disclosure of relevant information about the research, assurance of patient understanding of the information, and the patient's voluntary agreement to participate. Research staff will explain the study to potential participants and answer questions. If questions cannot be answered by research staff, the PI ([name]) will be consulted to answer additional questions.

Participants will be informed that their decision whether or not to participate in the study would not affect the medical care they receive at the VA in any way. Participants will be informed that participation will involve completing frequent, serial e-Questionnaires using their own personal electronic devices (PC, tablet, or smartphone) over a 1-year period of follow-up. All data collection after the time of recruitment will involve these electronically administered e-Questionnaires. E-Questionnaires will include questions on sociodemographics, back specific functional status, pain, physical activities, health-related quality of life, mood, stress, and other study measures. Participants will be informed that joining the study is entirely optional.

Potential candidates will also:

- i. Receive detailed information concerning the overall study goals from a research staff member. It will be explained that participants' involvement in this observational study will not affect their medical care at the VA in any way.
- ii. Receive adequate time to raise questions and voice concerns.

iii. Be questioned to assure that they understand all information provided. Potential participants will be asked to repeat back understanding of this material, as necessary. Individuals will not be permitted to participate if there is any question as to whether a person is able to provide informed consent.

iv. Potential participants will be provided with as much time as needed to review the Information Statement and ask the research staff member questions about the Information Statement, their rights as participants, and participation in the study. Potential participants will be fully informed of all risks and benefits prior to giving their verbal informed consent and prior to enrollment in the study. Participants will be asked if they need some time to consider their involvement before providing consent. If so, a time will be scheduled to continue the discussion at a later date using Recruitment Mode 2 (telephone), or participants will be asked to call research staff using the study telephone number, if they wish to complete informed consent and participate in the study in the future.

iv. Following the above, potential participants will provide verbal consent to participate in the study procedures.

v. If informed consent procedures are being performed remotely by telephone interactions with research study staff (as in Mode 2 described above), the information packet sent to Veterans recruited in this manner will contain 1 copy of the Information Statement. The Information Statement can be retained by the participant for their records.

vi. Be informed about the run-in period requirements (see above in section 5).

During the informed consent process, study staff will explain to potential participants that participation in the VA component of this study will (1) involve data collection within the VA, which will produce VA data that will not subsequently leave the VA; and (2) **data collection outside the VA. Data collected outside the VA will later be downloaded to the VA, at which point it becomes VA data and will not subsequently leave the VA during the study.** The informed consent process (and the Information Statement submitted with this application) will briefly describe study processes involved with the non-VA component of this study, while clarifying that the VA informed consent process potential participants are completing at the time does not cover or apply to the non- VA component of the study.

During informed consent study staff will clarify the following

(1) Data collection within the VA will include several parts:

- a. Information needed for participant screening, including the initial conversation between Veteran and research study staff, and subsequent interactions until and including informed consent.
- b. Obtaining participants VA electronic medical record data from existing administrative data sources (e.g. CPRS, Vista, the Corporate Data Warehouse [CDW], Cerner, etc.). This data will be used for analyses at VA, and will not leave the VA.
- c. Any data obtained from sources outside the VA (as described immediately below) that enters the VA. Once such data enters the VA, it becomes VA data and subsequently will not leave the VA.

(2) Data collection outside the VA will include the following:

- a. Electronic survey data collection conducted by a non-VA private company (DatStat, Inc.) specializing in secure HIPPA-compliant electronic data collection using participants' own personal electronic devices (smartphone, tablet, and/or PC). e-Questionnaires will not include sensitive medical information. e-Questionnaires will involve self-reports of pain, physical limitations, physical activities, mood, and recent treatments for low back pain.
- b. This component of electronic data collection will be led by researchers at the University of Washington (UW). The involvement of UW will entail a separate informed consent process for UW.

The consent process for VA research processes will occur at a time deemed mutually feasible for the Veteran patient and staff member and coordinated on a case-by-case basis. If the consent process is conducted by Mode 1 (in-person), we will follow the processes described above in section 5.2.1 to ensure that the staff-patient discussions take place in a private location at VAPSHCS (e.g., a medical

exam room or private conference room) or another location where a private discussion can be ensured. If the consent process is conducted by Mode 2 (telephone), the VAPSHCS research staff member will make the telephone call from a VAPSHCS telephone in a private room to minimize the possibility of coercion or undue influence. Prospective subjects will be informed that all study personnel will have completed the necessary human subjects protections training per VA policy. Informed consent will be conducted in English. Prospective subjects will be asked if they are able to understand English and whether they feel comfortable speaking it.

If during the course of this contact the potential participant has questions that cannot be addressed by research staff, another research staff member, the PI, or another study investigator will follow up with the potential participant to answer the questions. Potential participants may take time to think about participating and render a decision at a future time.

A waiver of HIPAA authorization has been approved for all study procedures, which allows the research team to view and analyze participant administrative data (CPRS, Cerner, or other data sources maintained by the VA) for the purposes of recruitment. In addition, the waiver of HIPAA authorization allows for analyses of VA administrative data for those individuals who do not respond to mailing packets, for the purpose of weighting the study sample of participants back to represent the target population of Veterans who were participants and those who did not respond to the mailing. The waiver of HIPAA authorization does NOT apply to individuals who contact the study to opt out of the study, or to participants who contact the study but decide not to participate in the study.

The same general study-related information content provided by study staff at the screening visit/informed consent will also be made available to participants throughout the study period on the participant-facing website Participant Portal (the 'FLAReS' website, or [flares.datstat.com/portal/](http://flares.datstat.com/portal/)), which will be run by the non-VA (UW) component of this research study. The FLAReS website was set up by the private (non-VA) data collection company mentioned earlier (DatStat/R1) specializing in secure HIPAA-compliant electronic questionnaire administration, and processes related to the website will be covered through the UW component of the proposed research and the related UW human subjects processes.

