### **Description of Potential Risks and Risk vs. Benefit**

Both VA and non-VA components of this study are entirely observational. Risks pertaining to the VA component of this research study involve those related to the obtaining, storage, and analysis of VA research data, and any possible inadvertent disclosures.

**Physical risks:** Participants who wear ActiGraphs may find it uncomfortable or inconvenient in general to wear the ActiGraph during the day or while sleeping. There is no risk of electrical shock while wearing the activity monitor. The Actigraph will not be able to track where participants are physically located. Participants may experience sweating or skin irritation while wearing the activity monitor if they have sensitive skin. We will provide participants with tips on how to mitigate any discomfort or inconvenience due to the positioning/wear of the unit, such as shifting the unit positioning when feasible.

**Psychological risks:** Participants may experience fatigue and/or boredom while completing the research assessments. Some participants may also experience mild anxiety, frustration, and/or stress while reporting on their pain and mood during the research assessments.

**Social, Legal, Privacy, and Other Risks:** There are research risks to participants’ privacy associated with inappropriate disclosure of data. Specifically, there is a risk that a participant’s identity and participation in the study may be discovered by an outside party. However, we will take steps as described elsewhere in this document to ensure that the likelihood of such risk is negligible.

Risks pertaining to the non-VA component of this research study also involve those related to the obtaining, storage, and analysis of non-VA research data, and any possible inadvertent disclosures. Such risks relevant to the non-VA component of the research are covered in the separate human subjects approvals processes at UW, and also in the “Summary of UW Research” (Attachment S) provided as part of the VA research processes so that VA participants are aware from the start of both VA and non-VA components of the overall research. Following any future substantive modifications to the UW IRB application (for example, study staff modifications at UW would not be considered substantive), we will provide the relevant updated UW IRB documentation (including participant-facing materials) and approvals back to the VAPSHCS IRB.

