- *The Single-item Global Measure of Depression* This single-item self-report measure of depression has been validated as compared to the Clinically Useful Depression Outcome scale, which involves 16 items assessing the DSM-IV inclusion criteria for major depressive disorder.
- *Post-traumatic stress disorder (PTSD) Checklist, civilian version (PCL-C):* The PCL is a standardized self-report rating scale for PTSD comprising 17 items that correspond to the key symptoms of PTSD.

- *Single-item stress question (SISQ)* The SISQ has been shown to have content, criterion, and construct validity in comparison to comprehensive measures of stress, well-being, psychological symptoms, and sleep disturbances.
- *Chronic Pain Acceptance Questionnaire*: This 20-item scale was designed to measure acceptance of pain. The acceptance of chronic pain is thought to reduce unsuccessful attempts to avoid or control pain and thus focus on engaging in valued activities and pursuing meaningful goals.
- *UW Pain Self-efficacy Questionnaire*: This questionnaire was developed to assess the confidence people with ongoing pain have in performing activities while in pain (<https://uwcorr.washington.edu/measures/uw-prse/>).
- *Medications*: Patients will report medications they have taken for pain in the past 24 hours.

Other variables to be included in the baseline e-Questionnaire include: low back pain history characteristics, work-related factors (receiving disability or compensation, or planned applications, hours/days off work at baseline, job satisfaction ratings, physical demands at work), smoking and vaping history, and questions with regards to current typical number of alcoholic beverages consumed per week and cannabinoid use.

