### Scheduled e-Questionnaires

We have now provided an updated version of the Scheduled e-Questionnaire content (Attachment Q2-Scheduled e-Questionnaire). As mentioned above, this e-Questionnaire is part of the UW (non-VA) study processes. Only the *content* of the e-Questionnaire can be provided, not the actual e-Questionnaire, since it is an electronic questionnaire. Variables included in both Scheduled and Flare Window e-Questionnaires include several of the measures listed immediately above under "Baseline e-Questionnaire", such as: numerical rating scales of low back pain intensity, analgesic use, the 2-item version of the Coping Strategies Questionnaire, the 2-item version of the TSK, the 1-item global measure severity of depression, the 2-item version of the PCL-C scale, the single-item stress question (SISQ), hours of lost work, other variables related to work quality/quantity, recent cigarette smoking, vaping history, number of alcoholic beverages consumed and cannabinoid use.

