## 6.0 Reporting

There are no study-related processes in this purely observational study that would be expected to cause serious adverse events. [E-Questionnaires inquire about musculoskeletal pain conditions and treatments, other diagnoses, sociodemographic factors, and factors related to healthy living and lifestyle](#). We do not anticipate these to pose any significant effect on a participant's health or well-being, although it is theoretically possible (although highly improbable) that some questions may cause emotional distress or discomfort due to participants paying more attention to areas where musculoskeletal pain may or may not be present. Any possible discomfort or distress is expected to be negligible, and of note e-Questionnaires do not include question items pertinent to sensitive issues such as suicide risk, stigmatized behaviors, sexual trauma, etc. We will take the steps outlined in the IRQ to mitigate any possible discomfort or distress for participants when answering questions in the e-Questionnaires.

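### The VA consent text says the e-Questionnaires hold no sensitive medical information, yet they carry PTSD, depression, alcohol and cannabinoid items, so the privacy and distress risks are understated

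*Combined protocol and SAP*

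**What the plan says.** Section 5.3, A. Informed Consent, introduces a list with "During informed consent study staff will clarify the following". Under data collection outside the VA, by a private company, the list states: "e-Questionnaires will not include sensitive medical information". The next sentence describes the content: "e-Questionnaires will involve self-reports of pain, physical limitations, physical activities, mood, and recent treatments for low back pain". Earlier in the same subsection a broader list ends with "mood, stress, and other study measures".

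Section 6.0 says the forms "do not include question items pertinent to sensitive issues such as suicide risk, stigmatized behaviors, sexual trauma, etc". It attributes any distress to added attention to painful areas, calls that very unlikely, and rates it negligible.

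Section 5.1, Description of Potential Risks and Risk vs. Benefit, says some participants may feel mild anxiety, frustration or stress when reporting pain and mood. It describes the privacy risk as an outsider learning who the participant is and that he or she is in the study, with steps taken "to ensure that the likelihood of such risk is negligible".

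Section 5.5 gives the instruments. On the baseline form: "The PCL is a standardized self-report rating scale for PTSD comprising 17 items that correspond to the key symptoms of PTSD". That form also has a depression short form, a single depression item, weekly alcohol intake and cannabinoid use. The scheduled form includes a 2-item PTSD screen, the single depression item, a stress item, and "recent cigarette smoking, vaping history, number of alcoholic beverages consumed and cannabinoid use". The flare-window form has the same content.

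**The concern.** The sentence in Section 5.3 is categorical, and staff are to convey it during consent. A candidate told this, and then told that the forms cover pain, activities, mood and back treatments, would not expect a PTSD symptom checklist or repeated questions about alcohol and cannabinoids. The answers are first collected by a private non-VA company.

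At stake is the accuracy of the VA consent process. Section 5.3 itself makes disclosure of relevant information a condition of adequate consent, and commits to informing candidates fully of risks before they agree. Consent is verbal and its documentation is waived, so what staff say carries weight. The same premise also appears in the risk assessment in Section 6.0.

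**Working it through.** The plan gives no figure to reproduce. The check compares the texts, with a short count of exposure.

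**Step 1. Instruments against the consent description.**

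| Content | Baseline form (5.5) | Scheduled and flare-window forms (5.5) | Named in the Section 5.3 content lists? |
|---|---|---|---|
| PTSD symptoms | 17-item checklist | 2-item version | No |
| Depression | Short form and single item | Single item | Only as mood |
| Stress | Single item | Single item | Yes, in the earlier list only |
| Alcohol | Weekly intake | Number of drinks | No |
| Cannabinoids | Yes | Yes | No |
| Tobacco and vaping | Yes | Yes | No |

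PTSD and substance use appear in neither list. A catch-all for other measures does not disclose them, and it cannot offset an explicit statement that nothing sensitive is asked.

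**Step 2. Instruments against Section 6.0.** The denial there covers sensitive issues in general and gives suicide risk, stigmatized behaviors and sexual trauma as examples. The PTSD checklist and the cannabinoid item undercut it, although the examples leave room for argument. The paragraph's account of distress considers only attention to pain, and does not mention the PTSD or depression items.

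**Step 3. Section 5.1 against Section 6.0.** Section 5.1 accepts that some participants may feel mild anxiety or stress; Section 6.0 treats distress as very unlikely and negligible. The two need to be reconciled. In Section 5.1 the distress is tied to pain and mood reports, and the privacy risk to identity and participation. Exposure of mental-health or substance-use answers is not mentioned in either section.

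**Step 4. Exposure per participant (upper bounds).** Section 5.2.7 pays for up to 36 scheduled forms. Section 5.1 sets three a week in weeks 1 to 4.

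- Scheduled forms in the first four weeks: 3 × 4 = 12.
- Repeat PTSD item responses from scheduled forms: 36 × 2 = 72.
- With the baseline checklist: 17 + 72 = 89, before any flare-window form.
- Each flare-window form adds 2 more.

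These are counts of item responses and do not measure harm.

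**Step 5. Could the items be dropped instead?** Not without changing the analysis. Section 3.0 lists depression, stress and post-traumatic stress among the confounders and moderators for Aim 1, with the same framework for Aim 2, and Section 5.6.2a uses depression, PTSD and stress in the adjusted models. It is the text that has to change.

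**The case against.** The strongest reply is that the governing consent for these forms lies elsewhere. Section 5.3 says the VA consent does not extend to the non-VA component. Section 5.2.5 requires the UW consent before any questionnaire can be completed. Section 3.0 says Attachment S exists so that candidates understand both components from the start. None of those texts is available, and they may describe the PTSD and substance-use items in full. This limits what can be concluded, but it does not rescue the sentence: if those texts list the items, what staff say contradicts them; if they repeat the denial, the error spreads.

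A second reply is that the key terms are undefined. That is fair for a weekly drink count, and the sponsor could argue a narrow meaning. It is much harder to argue for PTSD symptoms, and candidates are given no definition.

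A third is that some disclosure exists: mood and stress are named in Section 5.3, mild anxiety and a privacy risk in Section 5.1, and other diagnoses and lifestyle factors in Section 6.0. This stands, and is why the risks are better called understated than wholly misstated. Nor was the content hidden from the IRB, since Section 5.5 lists the measures.

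Two stronger readings are tempting. One is that participants agreed to take part on a false assurance; the documents cannot show this, because most of what participants read is not in them. The other is that safety information is gathered ad hoc because of the mistaken premise. Section 6.0 does not link the two, and it refers to mitigation steps in the IRQ, which is also unavailable.

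**Conclusion.** The inconsistency is real and should be corrected. The Section 5.3 statement is inaccurate against the plan's own instrument list, the matching sentence in Section 6.0 is undercut by it, and the risk text in Sections 5.1 and 6.0 understates the privacy and distress risks and disagrees internally about distress.

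It applies to the consent process for all recruits, up to 730. The conclusion rests on two assumptions: that PTSD symptoms and cannabinoid use fall within the ordinary meaning of sensitive medical information, and that staff follow Section 5.3 as written. It is confined to the protocol text. It does not establish that any consent was invalid or that distress is poorly managed, and it has no bearing on sample size, power, alpha or the analyses.

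**What to change.** - **Section 5.3:** delete the sentence. State instead that the e-Questionnaires ask about PTSD and depression symptoms, stress, and alcohol, cannabinoid and tobacco use; that a non-VA company collects the answers; that they are downloaded to the VA; and that UW researchers keep de-identified, anonymized responses, as Section 9.0 provides. The new text should not suggest that non-VA holding ends at download.
- **Section 6.0:** correct the sentence on sensitive issues, and base the distress rating on the actual items.
- **Section 5.1, risk subsection:** extend the privacy risk to the content of the answers and the distress risk to the PTSD and depression items, and reconcile it with Section 6.0.
- **Information Statement, Attachment S and Participant Portal text:** make the same correction wherever they repeat the claim.

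The cost is one IRB amendment with notice to UW. No new data or procedure is needed. A few candidates may decline once told.
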